# 7.2. Participant Discontinuation/Withdrawal From the Study

A participant may withdraw from the study at any time at his/her own request. Reasons for discontinuation from the study include the following:

- Withdrawn consent (refused further follow-up);
- Lost to follow-up;
- Medication error without associated AE;
- Death;
- Study terminated by sponsor;
- AEs;
- Protocol violation;
- No longer meets eligibility criteria.

If a participant does not return for a scheduled visit, every effort should be made to contact the participant's parent(s)/legal guardian(s). All attempts to contact the parent(s)/legal guardian(s) and information received during contact attempts must be documented in the participant's source document. In any circumstance, every effort should be made to document participant outcome, if possible.

The parent(s)/legal guardian(s) should be questioned regarding the reason for the participant's withdrawal. The investigator or his or her designee should capture the reason for withdrawal in the CRF for all participants.

If a participant withdraws from the study, the parent(s)/legal guardian(s) may request destruction of any remaining samples taken and not tested, and the investigator must document any such requests in the site study records and notify the sponsor accordingly.

The parent(s)/legal guardian(s) should be requested to have the participant return for a final visit, if applicable, and the investigator will perform the procedures indicated for the next visit. Any AEs or SAEs that are continuing at the time of withdrawal from the study should be followed until resolution or, in case of permanent impairment, until the condition stabilizes.

If the participant withdraws from the study and his/her parent(s)/legal guardian(s) also withdraws consent (see Section 7.2.1) for disclosure of future information, no further evaluations should be performed and no additional data should be collected. The sponsor may retain and continue to use any data collected before such withdrawal of consent.

When a participant withdraws from the study because of an SAE, the SAE must be recorded on the CRF and reported on the Vaccine SAE Reporting Form.

Lack of completion of all or any of the withdrawal/early termination procedures will not be viewed as protocol deviations so long as the participant's safety was preserved.

Participants who have received the investigational product will not be replaced regardless of the reason for withdrawal.

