3.5. Safety Endpoints

3.5.1. Adverse Events

The relationship between (S)AEs and the investigational products will be characterized as related or not related as determined by investigators and as described in the protocol. The severity of AEs will be characterized as mild, moderate, and severe.

The time period for actively eliciting and collecting (S)AEs and NDCMCs for each participant is outlined in Table 5.

Visit Window	Visits 1-2	Visit 3-4
(Days)	Day 1 Through 28 to 42 Days After	270 to 300 Days After Visit 1 Through 28 to
	Visit 1	42 Days After Visit 3
Nonserious AEs	ICD through and including Visit 2	From Visit 3 through and including Visit 4
	(1 month after Dose 1)	(1 month after Dose 2)
SAEs	ICD through the end of study	
NDCMCs	ICD through the end of study	
Immediate AEs	Within the first 30 minutes of each dose	

Table 5. Summary of Adverse Event Collection

Abbreviations: ICD = informed consent document; NDCMC = newly diagnosed chronic medical condition.

An NDCMC is defined as a disease or medical condition not previously identified that is expected to be persistent or otherwise long-lasting in its effects.

The time period for actively eliciting and collecting AEs ("active collection period") for each participant/parent(s)/legal guardian begins from the time the participant/parent(s)/legal guardian provides informed consent, which is obtained before the participant's participation in the study (ie, before undergoing any study-related procedure and/or receiving investigational product), through and including Visit 2, and from Visit 3 through including Visit 4. SAEs and NDCMCs will be categorized according to MedDRA terms. NDCMCs and SAEs will be collected from the signing of the ICD through the end of the study. For participants who are screen failures, the active collection period ends when screen failure status is determined.

Medical occurrences that begin before consent will be recorded on the Medical History/Current Medical Conditions section of the CRF, not the AE section.

All events collected on the CRF will be categorized according to the current version of MedDRA (at the time of reporting).

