3.5.1.1. Analysis Intervals

There will be 6 analysis intervals for the AE data collected via the CRF (Table 6). The analysis populations used for these intervals are described in detail in Section 4.

#	Analysis Interval	Analysis Population	Interval Start Date (Inclusive)	Interval Stop Date (Inclusive)	Safety Data
1	Within 30 days after Dose 1	Dose 1 safety	Vax 1 date	Vax 1 date + 30 days	AEs, SAEs, NDCMCs
2	Within 30 days after Dose 2	Dose 2 safety	Vax 2 date	Vax 2 date + 30 days	AEs, SAEs, NDCMCs
3	Within 30 days after any dose	Safety	Vax 1 date or Vax 2 date	Vax 1 date + 30 days or Vax 2 date + 30 days	AEs, SAEs, NDCMCs
4	From 1 month after Dose 1 through 9 months after Dose 1	Dose 1 safety	Visit 2 date	Visit 3 date	SAEs, NDCMCs
5	From Dose 1 through 9 months after Dose 1	Dose 1 safety	Vax 1 date	Visit 3 date	SAEs, NDCMCs
6	Throughout study	Safety	Vax 1 date	Visit 4 date	SAEs, NDCMCs

 Table 6.
 Analysis Intervals for AEs, SAEs, and NDCMCs

Abbreviations: NDCMC – newly diagnosed chronic medical condition.

Two analysis intervals will be applied to immediate AEs (Table 7).

 Table 7.
 Analysis Intervals for Immediate AEs

#	Analysis Interval	Analysis Population	Interval Start Date/Time (Inclusive)	Interval Stop Date/Time (Inclusive)
1	Dose 1	Dose 1 safety	Vax 1 time	Vax 1 time + 30 minutes
2	Dose 2	Dose 2 safety	Vax 2 time	Vax 2 time + 30 minutes

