4. ANALYSIS SETS (POPULATIONS FOR ANALYSIS)

Data for all participants will be assessed to determine if participants meet the criteria for inclusion in each analysis population prior to unblinding and releasing the database. Classifications will be documented per standard operating procedures.

Population	Description
Enrolled	All participants, or participant's parent(s)/legal guardian(s), who sign the ICD.
Evaluable	Defined according to post–Dose 1 evaluable and post–Dose 2 evaluable criteria.
mITT	Defined according to post-Dose 1 and post-Dose 2 criteria.
Safety	All enrolled participants who receive at least 1 dose of the investigational product and have safety data reported after vaccination.

Defined Population for Analysis	Description	
Post-Dose 1 evaluable immunogenicity	1. Were enrolled and eligible through Visit 2.	
population	2. Received the investigational product at Visit 1.	
	3. Had blood drawn for assay testing within the required time	
	frames at Month 0 (Visit 1; before Dose 1) and Month 1	
	(Visit 2; 1 month after the Dose 1: window 28-42 days).	
	4. Had at least 1 valid and determinate MenA, MenC,	
	MenW-135, and MenY assay result at Visit 2 (1 month	
	after Dose 1).	
	5. Had received no prohibited vaccines or medications through	
	Visit 2.	
	6. Had no major protocol deviations through Visit 2.	
Post–Dose 2 evaluable immunogenicity	1. Were enrolled and eligible through 1 month after Dose 2 of	
population	Nimenrix.	
	2. Received the investigational products at Visit 1 and Visit 3.	
	3. Had blood drawn for assay testing within the required time	
	frames at Month 0 (Visit 1; before Dose 1) and at 1 month	
	after Dose 2 (Visit 4; 1 month after Dose 2: window 28-42	
	days).	
	4. Had at least 1 valid and determinate MenA, MenC,	
	MenW-135, and MenY assay result at Visit 4 (1 month after	
	Dose 2).	
	5. Had received no prohibited vaccines or medications through	
	Visit 4.	
	6. Had no major protocol deviations through Visit 4.	
Post–Dose 1 mITT	All participants who received at least 1 dose of Nimenrix and	
	had at least 1 valid and determinate MenA, MenC, MenW-135,	
	and MenY assay result available at Visit 2.	
Post–Dose 2 mITT	All participants who received 2 doses of Nimenrix and had at	
	least 1 valid and determinate MenA, MenC, MenW-135, and	
	MenY assay result available at Visit 4.	

Defined Population for Analysis	Description

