Dose 1 safety population	This population will include participants who received the first dose of investigational product at Visit 1 and for whom safety information is available from Visit 1 to prior to Visit 3.
Dose 2 safety population	This population will include participants who received the first and second dose of investigational product at Visit 1 and Visit 3 and for whom safety information is available from Visit 3.

For determination of the evaluable immunogenicity population(s), Items 1 through 4 will be computerized checks of the data, while Items 5 and 6 will be determined by clinical review. A major protocol violation is a protocol violation that, in the opinion of the sponsor's global medical monitor, would materially affect assessment of immunogenicity (eg, participant receipt of a prohibited vaccine or medication that might affect immune response or a medication error with suspected decrease in potency of the vaccine). The sponsor's global medical monitor will identify those participants with a protocol violation prior to the immunogenicity analysis performed for the study.

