5.3. Methods to Manage Missing Data

5.3.1. Safety Data

Standard algorithms on handling missing AE start dates will be applied according to Pfizer safety rules. No other missing information will be imputed in the safety analysis.

PFIZER CONFIDENTIAL
Page 28

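### SAP Table 6 closes the long SAE and NDCMC intervals on visit dates that early leavers may not have, and counts a same-day event after Dose 2 towards Dose 1 as well

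*SAP*

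**What the plan says.** SAP 3.5.1.1, Table 6, defines six intervals by a start date and a stop date, both inclusive.

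- Intervals 1 to 3 run for 30 days from a dose. Interval 1, for example, stops at "Vax 1 date + 30 days".
- Interval 4, "From 1 month after Dose 1 through 9 months after Dose 1", starts on the Visit 2 date and stops on the Visit 3 date.
- Interval 5, "From Dose 1 through 9 months after Dose 1", starts on the date of the first vaccination and stops on the Visit 3 date.
- Interval 6, the whole study, starts on the date of the first vaccination and stops on the Visit 4 date.

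Intervals 4 to 6 cover SAEs and NDCMCs only. Intervals 4 and 5 serve secondary endpoints; interval 6 serves an exploratory endpoint added in the SAP.

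The denominator for intervals 4 and 5 is the Dose 1 safety population. SAP 4 defines it as infants given Dose 1 and "for whom safety information is available from Visit 1 to prior to Visit 3". The denominator for interval 6 is the safety population: "All enrolled participants who receive at least 1 dose of the investigational product and have safety data reported after vaccination".

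On missing data, SAP 5.3.1 applies standard algorithms to missing AE start dates and then says "No other missing information will be imputed in the safety analysis".

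**The concern.** A visit date exists only for an infant who attends the visit. One who dies, is lost to follow-up or refuses a final visit before Visit 3 has no stop date for intervals 4 and 5. One who leaves between Visits 3 and 4 has none for interval 6. One who misses Visit 2 has no start date for interval 4. Neither safety population requires the closing visit, so an early leaver with some safety data still counts in the denominator, and Protocol 7.2 does not allow vaccinated infants to be replaced.

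If a program tests whether the onset date lies between start and stop, and a blank stop fails the test, the infant is counted as having had no event. The percentages would then be too low, and a death, which is an SAE by definition, is the clearest case.

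A second fault needs no dropout. Protocol 5.5.1 puts the Visit 3 blood draw and Dose 2 on the same day. Because the stop date is inclusive, an SAE arising after Dose 2 on that day falls in intervals 4 and 5, which describe Dose 1, and in interval 2, which describes Dose 2.

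**Working it through.** **1. Is a fallback written anywhere?**

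- SAP 3.5.1: "NDCMCs and SAEs will be collected from the signing of the ICD through the end of the study". This governs collection, not assignment to an interval. Protocol 4.4 defines the end of the study as one date for the whole study, so it gives no stop date for an individual infant.
- Protocol 8.3.1 ends collection when consent is withdrawn. Table 6 does not carry this over.
- Protocol 7.2: "When a participant withdraws from the study because of an SAE, the SAE must be recorded on the CRF". The event is therefore in the data, but nothing places it in a Table 6 interval.
- Protocol 7.2 asks that a withdrawing infant return for a final visit where applicable. The SAP does not say whether that date serves as the Visit 3 or Visit 4 date.
- SAP 6.6.1.4 lists deaths. A listing does not add to a percentage.

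None of these closes the gap. The SAP does write fallbacks elsewhere: in SAP 3.4.1 the consent date replaces the Dose 1 date for infants not vaccinated, and Table 8 extends reactogenicity to the day of resolution.

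**2. Internal consistency.** Take a fatal SAE on Day 20. It counts in interval 1. Read literally, it has no closed interval 5, although interval 5 starts on the same date and is meant to run much longer. The report could show more infants with an SAE within 30 days than over 9 months.

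**3. The plan's own safety figure.** Protocol Table 5 gives the chance of at least one event among 150 infants. The formula 1 − (1 − p)^150 gives 0.139, 0.529, 0.779 and 0.952 for p = 0.1%, 0.5%, 1.0% and 2.0%. These match the printed 0.14, 0.53, 0.78 and 0.95. No printed figure is in dispute; the check confirms 150 as the denominator.

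**4. Effect of an omitted event (Clopper-Pearson, denominator kept at 150).**

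- One fatal SAE counted: 1/150 = 0.67% (0.02 to 3.66). Omitted: 0/150 = 0% (0 to 2.43); the upper limit is 1 − 0.025^(1/150).
- Three such events counted: 3/150 = 2.00% (0.41 to 5.73). All omitted: 0% (0 to 2.43).

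**5. Range under assumed rates.** The documents give no dropout rate and no SAE risk, so every input here is an assumption: d infants leave before Visit 3, SAE risk is 2% in completers and p = 2% to 20% in leavers, and every leaver's event is lost.

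- True = [0.02 × (150 − d) + p × d] / 150
- Reported = 0.02 × (150 − d) / 150

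| Leavers d (assumed share) | Reported | True, p = 2% to 20% |
|---|---|---|
| 3 (2%) | 1.96% | 2.00% to 2.36% |
| 8 (5%) | 1.89% | 2.00% to 2.96% |
| 15 (10%) | 1.80% | 2.00% to 3.80% |
| 22 (15%) | 1.71% | 2.00% to 4.64% |

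For d = 22 and p = 20%: (2.56 + 4.40)/150 = 4.64% against 2.56/150 = 1.71%. The share of infants with an SAE who are lost runs from 2% to 63% across the table. These are upper bounds for each row.

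**6. Same-day events.** The interval 4 and 5 stop date (Visit 3, inclusive) and the interval 2 start date (second vaccination, inclusive) are the same day. Dates alone cannot separate the two. Protocol 8.2 records the onset time of any AE on a vaccination day, so the separation is possible.

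**The case against.** A reader might infer that every fatal event before the closing visit is lost by construction, or that the infants at highest risk have no interval at all. The documents do not support either.

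- **The loss is not certain.** SAP 2 says programming rules are prepared separately, and they are not available here. A program that treats a blank stop date as open-ended loses nothing. The interval labels count time from Dose 1, and an SAE at 6 months plainly belongs under the interval 5 label.
- **Not every leaver lacks a date.** Protocol 7.2 requests a final visit at which the next visit's procedures are done. Under Protocol 7.1, infants who only stop vaccination remain in safety follow-up. The firm cases are deaths, losses to follow-up and refusals of a final visit.
- **Other outputs catch some events.** Intervals 1 to 3 do not depend on follow-up visits, deaths are listed, and an infant who leaves after Visit 3 has complete intervals 4 and 5 if Visit 2 was attended. Interval 4 properly excludes events before Visit 2.
- **The size is not known.** The 15% in Protocol 9.2 is an allowance for exclusion from the immunogenicity evaluable population, which has causes other than dropout. It is not a dropout rate. A higher SAE risk in living dropouts is an inference.
- **The stakes are limited.** The study is descriptive, and the endpoints concerned are secondary or exploratory.

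All of this limits the claim, but it does not supply the missing rule. Two programmers could both follow Table 6 and report different SAE percentages, and one of those readings leaves deaths out. The same-day overlap is independent of these objections.

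**Conclusion.** The concern holds as a gap in the definition of intervals 4 to 6. Visit-date limits without a fallback, denominators that keep early leavers, and a bar on other imputation together mean that, read literally, SAEs and NDCMCs in infants without the closing visit meet no closed window. The possible bias is downward, in the secondary 9-month percentages and the exploratory whole-study percentage. Its size cannot be fixed from the documents: it is nil if blank stop dates are treated as open-ended. Otherwise each affected infant lowers the percentage by 1/150, or 0.67 points, if all 150 infants are in the denominator.

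The double counting of a same-day SAE after Dose 2 follows directly from the inclusive dates. It works in the other direction, adding to the Dose 1 percentages.

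Intervals 1 to 3, and with them the primary endpoint within 30 days after Dose 2, are not affected by missing visit dates. The point should be corrected before analysis, but it does not threaten the primary results.

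**What to change.** Add a footnote to SAP Table 6 with three rules.

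1. **Stop date, intervals 4 to 6:** the date of the scheduled visit if attended, otherwise the date of death, withdrawal or last contact. For an infant who misses Visit 3 but stays in the study, say whether later events still count towards the 9-month intervals.
2. **Start date, interval 4:** a stated rule for infants who missed Visit 2. Attendees start on a visit date between 28 and 42 days after Visit 1, so the footnote should make clear where a different rule applies.
3. **Dose 2 cut-off:** end intervals 4 and 5 immediately before the Dose 2 injection, using the onset time that Protocol 8.2 already requires for events on a vaccination day.

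The cost is one footnote and a small programming change. Onset times are already collected; I assume that dates of death, withdrawal and last contact are held in the study records. No added visit or procedure is needed.

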3.5.2. Reactogenicity Data

Reactogenicity data are solicited AEs. The reactogenicity data collected from the study e-diary will include: local reactions (redness, swelling, and pain at the injection site), systemic events (fever, decreased appetite, drowsiness, and irritability), and use of antipyretic medication.

The e-diary will record reactogenicity data from Day 1 to Day 7 following investigational product administration (Day 1 is the day of vaccination). Local reactions at the site of

PFIZER CONFIDENTIAL	
Page 19	

investigational product administration will be recorded (sites will be asked to administer Nimenrix into the left thigh of participants).

Three analysis intervals will be applied to reactogenicity data (Table 8).

#	Analysis Interval	Analysis Population	Interval Start Date (Inclusive)	Interval Stop Date (Inclusive)
1	Dose 1	Dose 1 safety	Vax 1 date	Vax 1 date + 6 days (or until resolved day)
2	Dose 2	Dose 2 safety	Vax 2 date	Vax 2 date + 6 days (or until resolved day)
3	Any dose	Safety	Vax 1 or Vax 2 date	Vax 1 or Vax 2 date + 6 days (or until resolved day)

 Table 8.
 Analysis Interval for Reactogenicity Data

3.5.2.1. Local Reactions Endpoints

For each local reaction, the derivation of whether or not the specific reaction occurred on each day and "any day (Days 1 through 7, where Day 1 is the day of vaccination)" will be made. The variable will be calculated for each vaccination as well as overall reactions for any vaccination. The derivation of this variable is given in Table 9.

Table 9.Derived Variables for Local Reactions

Variable	Yes (1) ^a	No (0)	Missing (.)
Each day (Days 1-7)	Participant/parent/legal guardian reports the reaction as "mild," "moderate," or "severe" on each individual day.	Participant/parent/legal guardian reports the reaction as "none" on the individual day.	Participant did not report on the reaction on the individual day.
Any day (Days 1-7)	Participant/parent/legal guardian reports the reaction as "mild," "moderate," or "severe" on any day (Days 1-7).	Participant/parent legal guardian reports the reaction as "none" on all 7 days or as a combination of "none" and missing on all 7 days.	Participant did not report on the reaction on any of the 7 days.

a. For redness and swelling, "mild," "moderate, and "severe" categories are based on the caliper size reported from the e-diary and defined in Table 10.

A caliper (measuring device) is used to measure the redness or swelling of the injection site area. Caliper units (range: 1-14+) are converted to centimeters according to 1 caliper unit = 0.5 centimeters and then categorized as none, mild, moderate, or severe based on the grading scale of local reactions in Table 10. Pain at the injection site will be assessed by the participant's parent(s)/legal guardian(s) according to the grading scale in Table 10.

PFIZER CONFIDENTIAL
Page 20

Only an investigator is able to classify a participant's local reaction as Grade 4, after physical examination of the participant or documentation from another medically qualified source (eg, emergency room or hospital record). Grade 4 will not be collected in the e-diary but will be collected as an AE on the CRF.

Local Reaction	Mild	Moderate	Severe	
	(Grade 1)	(Grade 2)	(Grade 3) ^a	Grade 4 ^b
Pain at injection site (tenderness)	Hurts if gently touched (eg, whimpers, winces, protests, or withdraws)	Hurts if gently touched with crying	Causes limitation of limb movement	Emergency room visit or hospitalization for severe pain (tenderness) at
				injection site
Redness	1 to 4 measuring device units = >0 to 2.0 cm	5 to 14 measuring device units = >2.0 to 7.0 cm	>14 measuring device units = >7.0 cm	Necrosis or exfoliative dermatitis
Swelling	1 to 4 measuring device units = >0 to 2.0 cm	5 to 14 measuring device units = >2.0 to 7.0 cm	>14 measuring device units = >7.0 cm	Necrosis

 Table 10.
 Local Reaction Grading Scale

Abbreviations: CRF = case report form; e-diary = electronic diary.

Note: If the size of the redness and/or swelling falls between 2 measuring device units, the higher measuring device unit number will be recorded in the e-diary.

- a. Parent(s)/legal guardian(s) of the participants experiencing local reactions >14 measuring device units (>7.0 cm) are to be contacted by the study site. An unscheduled visit may be required.
- b. A Grade 4 assessment should be made by the investigator. A Grade 4 reaction will not be collected in the e-diary but will be recorded as an AE on the CRF. The severity of the local reaction should be graded using the AE grading scale.

The maximum severity (highest grading) of each local reaction within 7 days after vaccination will be derived for each vaccination as well as any vaccination. The maximum severity will be derived as follows:

- = ., if values are missing for all days (Days 1 to 7);
- = 0, if the participant's parent(s)/legal guardian(s) reports all reactions as "none" or a combination of "missing" and "none" for all days (Days 1 to 7);
- = *highest grade* (maximum severity) within 7 days after vaccination, if the answer is not "none" for at least 1 day.

For participants experiencing any local reactions (or those with derived reaction presence in Table 9), the maximum duration (last day of reaction – first day of reaction + 1) will be derived for the study vaccination. Resolution of the event is the last day on which the event is recorded in the e-diary or the date the event ends if it is unresolved during the participant

PFIZER CONFIDENTIAL	
Page 21	

diary-recording period (end date collected on the CRF), unless chronicity is established. If there is no known end date, the duration will be considered unknown and set to missing.

For reactions that continue into the next vaccination visit, the duration will be calculated in a segmented fashion. The reaction end date will be set to the day prior to the next vaccination and will have a new start date as the day of next vaccination. The duration will be calculated separately from the new start date to the date of resolution. Participants with reactions spanning multiple vaccination visits will be included in a footnote.

Participants with no reported reaction have no duration.

The onset day of each local reaction will be derived. The onset day is defined as the first day of reporting the reaction with any severity after vaccination.

In summary, the following variables will be derived for local reactions:

- 1. Each local reaction on each day (Days 1 to 7) after each vaccination.
- 2. Each local reaction on any day (Days 1 to 7) after each vaccination and any vaccination.
- 3. Any local reaction on any day (Days 1 to 7) after each vaccination and after any vaccination.
- 4. Maximum severity of each local reaction on any day (Days 1 to 7) after each vaccination and any vaccination.
- 5. Maximum duration of each local reaction after each vaccination.

